We will specifically exclude pediatric ankle fractures in children under 18 years-of-age, tibial plafond (pilon) fractures in children and adults, medial malleolar osteotomies to access the talus, perform an ankle fusion, or deal with a pathologic lesion, osteonecrosis, or infection due to their diversity in diagnosis, management, and weight bearing status. Patients with prior surgical treatment of the ankle for fracture, deformity, infection, neoplasia, or other pathologic process on the ipsilateral extremity will also be excluded.

Patients that are non-weight bearing on one or both lower extremities prior to sustaining their ankle injury will be excluded.

Randomization

All elective and emergent admissions to Stanford Hospital and Clinics and Kaiser Permanente – South Sacramento that meet our inclusion/exclusion criteria will be identified and solicited for consent. Patients will be randomized by sealed envelope to surgical fixation with traditional headed screws, plates, and wires or Acutrak headless compression screws. At the time of randomization, the fracture pattern and severity, past medical history and medications, and demographic data will be documented.

Follow-up Protocol

After operative fixation, patients will receive fracture follow-up with a clinical evaluation for tenderness, radiographs to evaluate stability and union at 2 weeks, 6 weeks, 3 months of surgery and complete the PROMIS and VAS pain scores. Patients will be followed by telephonically once the fracture union is confirmed radiologically by the operating surgeon at 6 months, 1 year, and 2 years after surgical fixation. The VAS pain scores will be administered telephonically and the PROMIS questionnaires will be mailed to the patients (Table 1).⁹

Table 1: Protocol Summary

Time and Event Table	Injury/Office	2 weeks	6 weeks	3 months	6 months (over Telephone & mail)	1 year (over Telephone & mail)	2 years (over Telephone & mail)
Discuss Study	X						
Screening Log	X						
Informed Consent	X						
Eligibility Worksheet	X						
Demographic Data	X						
Medical History	X						
Randomization	X						
Clinical Assessment							
•Medial Ankle Tenderness	X	X	X	X	X	X	X
•Lateral Ankle Tenderness	X	X	X	X	X	X	X
Patient Reported Outcomes							
•PROMIS Score	X	X	X	X	X	X	X
•VAS Pain (by location)	X	X	X	X	X	X	X
•On Narcotics (yes/no)	X	X	X	X	X	X	X
Radiographs							
•Anterior-to-Posterior Ankle	X	X	X	X	-	-	-
•Lateral Ankle	X	X	X	X	-	-	-
Operative/Device	X						

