Removal of Hardware		X	X	X	X	X	X
Adverse Event	X	X	X	X	X	X	X
End of Study							X

Criteria for Removal of Hardware

Hardware may be removed if there is a surgical indication or patient/surgeon preference for removal. Patients will be asked whether they feel bothersome sensitivity at the both medial and lateral malleolus. If they mention sensitivity to light touch that is not bothersome they should not be subjected to hardware removal unless by patient or surgeon preference and noted as medial or lateral hardware removed for preference. On the other hand, if they mention bothersome sensitivity, it would be rated on a 0-5 Likert intensity scale. All bothersome sensation will be subjected to hardware removal and noted as removal for sensitivity. Other reasons for hardware removal indications include infection and non-union or mal-union requiring revision open reduction and internal fixation. The location of symptoms and reason for hardware removal should be specified and documented.

Documentation of Fracture Union

Union will be defined as a pain free fracture site on examination with evidence of radiographic healing and a return to full weight bearing confirmed by the operating surgeon

Power Analysis and Statistics

Retrospective review of ankle hardware removal cases indicates that 6% (8/126) of patients have their hardware removed for non-pain issues (e.g., infection, etc.) at 6 months and 17% (22/126) of patients have their hardware removed for pain on the medial or lateral side of the ankle at 6 months.⁸ Hence, the overall rate of hardware removal is 24% but if we can reduce half of the medial hardware removals the overall rate would be 14.5%. To detect this 9.5% difference, it would take 424 randomized patients (alpha = 0.05, and 80% power). Medial hardware removal will be prohibited for lateral hardware pain.

Utilizing the STRIDE database available at Stanford University, there have been 155 procedures involving fixation of the medial malleolus (CPT: 27766, 27814, 27822, 27823) over the past three years. Assuming a similar procedure burden at the other major Level I Trauma center and extrapolating this three-year data, we estimate the capability to enroll 500 patients over three years.

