All continuous variables will be reported as the mean and errors are reported as standard deviation. All categorical variables will be reported as the subset number and percentage of the total. Comparisons will be performed with the appropriate statistical test when indicated. Statistical significance will be set at p less than 0.05 with an appropriate Bonferroni correction for multiple comparisons when indicated.

Budget

The vast majority of the budget will go toward an experienced fulltime clinical research coordinator, level II (CRCII, Table 2). This person is critical to our success. Appropriately, some funds will be devoted to insuring the proper training and certification for the CRCII involved in this project as well as supply adequate computing power and meet secure data storage needs. Some funds would be used by the principal investigator and co-investigators to offset local travel and travel to national and international meetings to present the findings of this interdisciplinary work, including the American Academy of Orthopaedic Surgeons (AAOS), the Orthopaedic Trauma Association (OTA), and the American Orthopaedic Foot and Ankle Society (AOFAS).

Table 2: General Budget

Expense			Effort	Cost
Personnel	Principal Investigator	[name]	10%	\$36,000/year
	Co-Investigator	[name]	3%	\$10,000/year
	Co-Investigator	[name]	3%	\$10,000/year
	Co-Investigator	[name]	3%	\$10,000/year
	Co-Investigator	[name]	3%	\$10,000/year
	Co-Investigator	[name]	3%	\$10,000/year
	CRCII	TBD: Stanford	100%	\$90,000/year

	CRCII	TBD: 3 rd center	75%	\$68,000/year
	CRCII	TBD: Kaiser	75%	\$68,000/year
Equipment	Computers			\$3,000/year
	Secure Storage			\$1,000/year
Training				\$5,000/year
Travel	Society Meetings			\$5,000/year
	Between Sites			\$5,000/year
				\$275,000/year

Acumed Study Summary	
Company	Stanford University
Title	Prospective, multi-center, randomized, controlled study evaluating the union rate, rate of medial malleolus hardware removal and clinical outcomes after medial malleolus fracture fixation with Acutrak headless compression screws
Short Title	Acutrak Fixation of Medial Malleolus Fractures
Protocol Number	
Treatment Device	Acutrak headless compression screws
Control Device(s)	Mini-fragment Plating, Antiglides Plating, Headed Unicortical Screws, Headed Bicortical Screws, Tension Band Wiring

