Intended Use	The Acutrak headless compression screws are intended to provide fixation and anatomically reduce fractures of the medial malleolus that occur via supination-external rotation, pronation-external rotation, or pronation-abduction resulting in an oblique fracture pattern as well as supination-adduction resulting in a vertical shear fracture pattern.
Study Purpose	The fixation provided by the Acutrak headless compression screws provide sufficient fixation to achieve union and a favorable clinical outcome in both horizontal and vertical medial malleolus fractures when compared to bicortical and unicortical screw fixation, tension band wiring, and mini-fragment or buttress plating. However, minimizing the amount of dissection required for implantation as well as lack of prominent hardware surfaces will reduce the incidence and severity of hardware related pain and correspondingly the necessity of hardware removal.
Study Objectives	
Primary:
 
 • A successful outcome would be a reduction in the rate or severity of hardware related pain localized to the medial malleolus reducing the incidence of hardware removal from the medial malleolus at one year after sustaining an ankle fracture.
	
Secondary:
 
 • Another successful outcome would be an equivalent radiographic and clinical union rate when compared to traditional fixation methods. • Another successful outcome would be an equivalent PROMIS scores when compared to traditional fixation methods.

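### One-year hardware removal: no record source is named and no rule says how a patient not reached is counted; a record check and a censoring-aware estimate would close the gap cheaply

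*Combined protocol and SAP*

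**What the plan says.** - **Endpoint.** The Study Objectives row of the study summary describes success as less hardware-related pain at the medial malleolus, "reducing the incidence of hardware removal from the medial malleolus at one year after sustaining an ankle fracture".
- **Contact mode.** Follow-up Protocol: "Patients will be followed by telephonically once the fracture union is confirmed radiologically by the operating surgeon at 6 months, 1 year, and 2 years". Table 1 heads the corresponding column "1 year (over Telephone & mail"). The last scheduled visit with radiographs is at 3 months.
- **What those contacts carry.** Follow-up Protocol: "The VAS pain scores will be administered telephonically and the PROMIS questionnaires will be mailed to the patients". It names no source for hardware removal, although Table 1 marks removal at all six post-operative time points, including 6 months, 1 year and 2 years.
- **Side and reason.** Criteria for Removal of Hardware: "The location of symptoms and reason for hardware removal should be specified and documented". It does not say from what document.
- **Reporting.** Power Analysis and Statistics, repeated in the Statistical Methods row: "All categorical variables will be reported as the subset number and percentage of the total". The total is not defined. The plan gives no analysis set, missing-data rule, censoring rule or allowance for loss.
- **Records.** For feasibility, the plan did query coded procedures: "Utilizing the STRIDE database available at Stanford University, there have been 155 procedures involving fixation of the medial malleolus".

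**The concern.** Removal is an operation. It leaves a dated record with side and indication, whether or not the patient later answers the telephone. The plan schedules its capture after 3 months only at remote contacts, and those are where patients are most easily lost. A removal in someone not reached may therefore go unrecorded, and the plan does not say whether that person stays in the denominator.

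The choice matters because the candidate rules err in opposite directions. If it is left open, it can be made after the data are seen. Loss that differs between arms would bias the comparison on which the removal superiority aim (Specific Aim 4) rests. Side and reason also need a reliable source, because they decide whether a removal is medial and whether it was for pain.

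**Working it through.** **Inputs from the plan (Power Analysis and Statistics):** removal 24% vs 14.5%, 424 randomized, alpha 0.05, 80% power. **Assumed:** 1:1 allocation (212 per arm); the two rates apply at one year with constant hazard; loss rates of 5% to 30%, because the documents give none.

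**1. The plan's figure.** With pooled variance, n per arm = [z(1−α)·√(2p̄q̄) + z(1−β)·√(p₁q₁+p₂q₂)]² / d². Here p̄ = 0.1925, 2p̄q̄ = 0.3109, p₁q₁+p₂q₂ = 0.3064 and d = 0.095. One-sided: (1.645×0.5576 + 0.842×0.5535)² / 0.009025 = 211.9, so 212 per arm and 424 in total, an exact match. Two-sided gives 270 per arm, or 540. So 424 corresponds to a one-sided test with no loss, and power below is one-sided: Φ([d√n − 1.645·√(2p̄q̄)] / √(p₁q₁+p₂q₂)) with n = 212.

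**2. Chance f that a lost patient's removal was seen before loss.** λ = −ln(1−p) per year: 0.2744 and 0.1567.
- Lost at 3 months: f = 1 − (1−p)^0.25 = 6.63% and 3.84%.
- Lost uniformly over months 3 to 12: f = 1 − (e^(−0.25λ) − e^(−λ)) / (0.75λ) = 15.61% and 9.27%.

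**3. Rule A: lost patients stay in the denominator as not removed.** Observed rate = (1−m)p + m·f, with m the share lost in each arm. At m = 20%:
- Uniform loss: 0.8×24 + 0.2×15.61 = 22.3%; 0.8×14.5 + 0.2×9.27 = 13.5%; difference 8.9 points.
- Loss at 3 months: 0.8×24 + 0.2×6.63 = 20.5%; 0.8×14.5 + 0.2×3.84 = 12.4%; difference 8.2 points.

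| Loss m | Uniform: difference, power | At 3 months: difference, power |
|---|---|---|
| 5% | 9.3 points, 79% | 9.2 points, 78% |
| 10% | 9.2 points, 79% | 8.8 points, 77% |
| 20% | 8.9 points, 77% | 8.2 points, 73% |
| 30% | 8.6 points, 76% | 7.5 points, 70% |

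In the extreme where every removal in a lost patient is missed, m = 20% gives 19.2% vs 11.6%, 7.6 points and 70.1% power.

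**4. Rule B: known removals are kept and lost patients without one are dropped.** Rate = [(1−m)p + m·f] / [(1−m) + m·f]. With m = 20% and uniform loss: 22.32/83.12 = 26.9% and 13.45/81.85 = 16.4%. Both rates are overstated, and the difference grows to 10.4 points.

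**5. Rule C: only patients followed to one year are analysed.** The rates are unbiased if loss is unrelated to removal, but at m = 20% one-sided power is 71.9%.

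**6. Unequal loss under Rule A, no true effect (24% in both arms), 10% lost in control and 30% in Acutrak.** Spurious difference = (0.30 − 0.10)×(24 − f).
- Uniform loss: 0.2×(24 − 15.61) = 1.7 points. The chance of declaring Acutrak better is about 11% at a nominal 5%.
- Loss at 3 months: 0.2×(24 − 6.63) = 3.5 points.

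Simulation of the 1.7-point case with Kaplan-Meier gave a difference near zero and a false-positive rate between 4.6% and 5.8%, where loss is unrelated to removal.

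**7. Sensitivity to timing.** The source figures behind 24% (8/126 and 22/126) are six-month figures. Suppose all removals occur by six months, with λ = −ln(1−p)/0.5. One third of uniform losses fall in months 3 to 6, so f = (1/3)[1 − (e^(−0.25λ) − e^(−0.5λ))/(0.25λ)] + (2/3)p = 22.18% and 13.35%. With m = 20%, Rule A then gives 23.6% vs 14.3%, or 9.4 points, which is almost no dilution.

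**The case against.** A reader might infer that the plan counts patients not reached as having no removal, so that its rates are certain to be too low. The documents do not say this. The reporting sentence is generic, covers every categorical variable and leaves the total undefined. It could equally mean patients with one-year status, and step 4 shows that one version of that reading errs upward.

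A reader might also infer that side and reason rest on patient recall by telephone. That is not supported either. The telephone is tied to the VAS and the mail to PROMIS, location and reason must be documented, and the Safety row promises continuous monitoring of adverse events and complications. Silence on the source is not a decision to rely on recall.

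Other points also stand:
- A removal missed at one year could surface at the 2-year contact, though only if that patient is reached.
- The equal-loss effect is modest and nearly vanishes if removals are early.
- Nothing in the documents suggests a threefold imbalance in loss.
- The projected enrolment of 500 would absorb about 15% loss relative to 424 (76/500). That protects power, not the counting rule.
- Kaplan-Meier is unbiased only if loss is unrelated to removal.
- The database is documented only for Stanford, among three listed sites, and was used there to count fixations, not removals.

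None of this supplies the missing source, denominator or rule for the primary time point.

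**Conclusion.** The point holds as a cheap improvement to the primary endpoint. It is not a demonstrated bias, and its direction is not fixed by the documents: Rule A understates both rates, Rule B overstates both, and Rule C costs power. At an assumed 20% equal loss with constant hazard, Rule A costs 0.6 to 1.3 points of the 9.5-point difference and about 3 to 7 percentage points of one-sided power, and less if removals are early. Unequal loss is the more serious risk, because it can create or hide a difference; 10% vs 30% is an illustration, not a forecast. All loss rates and the removal hazard are assumptions.

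**What to change.** 1. **Source.** At 1 and 2 years, the coordinators already in the budget check operative and procedure records at the treating site for every randomized patient. Date, side and reason come from the operative note. Keep the telephone call to catch removals done elsewhere.
2. **Estimate.** Among all randomized patients, estimate one-year removal by arm with Kaplan-Meier, using cumulative incidence for reason-specific removal. Report the difference between arms with a 95% CI in place of the generic percentage.
3. **Censoring.** Censor at the last date on which removal status is actually known from patient contact or a site encounter. A negative record search alone should not extend follow-up, because the hardware may have been removed at another hospital.
4. **Sensitivity.** Prespecify an analysis that varies the assumed removal rate in patients not reached, separately by arm.

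**Cost:** modest coordinator time, record access at each of the three sites, consent and HIPAA wording, and a few lines of analysis text. Kaplan-Meier by itself adds little power; the recovered records do that. Removals at outside hospitals in patients who are not reached may still be missed.

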Static load to failure testing our laboratory has challenged this observation in vertical medial malleolus fracture patterns as well.⁵⁻⁷ We recently demonstrated (manuscript submitted) superior stiffness (463 ± 91 N/mm) and load at 2 mm of ankle joint displacement (922 ± 297 N) with antiglide plate fixation versus unicortical screw fixation (111 ± 35 N/mm and 284 ± 51 N, respectively) and bicortical screw fixation (279 ± 30 N/mm and 429 ± 112 N, respectively) of vertical medial malleolus fractures ($p < 0.05$).

Superior fixation requires extensive dissection and fixation known to result in prominent hardware and hardware related pain. None of these fixation methods address the lack of soft tissue to cover the medial malleolus and the common practice of hardware removal to address post-fixation hardware pain. Retrospective review of ankle hardware removal cases indicates that 6% (8/126) of patients have their hardware removed for non-pain issues (e.g., infection, etc.) at 6 months and 17% (22/126) of patients have their hardware removed for pain on the medial or lateral side of the ankle at 6 months.⁸

The headless configuration of the Acutrak system makes it ideal for medial malleolus fixation and may obviate the need for hardware removal. We recently demonstrated (manuscript submitted) superior stiffness and load at 2 mm of ankle joint displacement of an Acutrak screw construct (244 ± 58 N/mm and 483 ± 91 N, respectively) when compared to partially threaded parallel unicortical cancellous screw construct (111 ± 35 N/mm and 278 ± 49 N, respectively) in static load

[figure not shown]

Figure 1: Vertical shear medial malleolus fractures fixed with cancellous screws (left) and Acutrak screws (right) demonstrating the lack of hardware prominence after fixation as well as maintenance of reduction after off-set axial loading.

to failure testing of vertical medial malleolus fractures. Additionally, when the specimens were displaced to 6 mm and allowed to relax, the Acutrak headless compression screw constructs reduced to the pretesting fragment alignment while the parallel cancellous constructs remained displaced (see Figure 1).

HYPOTHESIS

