The fixation provided by the Acutrak headless compression screws provide sufficient fixation to achieve union and a favorable clinical outcome in both horizontal and vertical medial malleolus fractures when compared to bicortical and unicortical screw fixation, tension band wiring, and mini-fragment or buttress plating. However, minimizing the amount of dissection required for implantation as well as lack of prominent hardware surfaces will reduce the incidence and severity of hardware related pain and correspondingly the necessity of hardware removal.

Specific Aims

- 1) *Prospectively establish equivalence with respect to fracture union rate after Acutrak headless compression screw fixation when compared to other fixation methods for medial malleolus fractures.*
- 2) *Prospectively establish equivalence with respect Patient Reported Outcome Measurement Information System (PROMIS) scores after Acutrak headless compression screw fixation when compared to other fixation methods for medial malleolus fractures.*
- 3) *Prospectively establish superiority with respect to hardware related pain after Acutrak headless compression screw fixation when compared to other fixation methods for medial malleolus fractures.*
- 4) *Prospectively establish superiority with respect to the hardware removal rate after Acutrak headless compression screw fixation when compared to other fixation methods for medial malleolus fractures.*

Study Design

Institutional Review Board and HIPAA

The institutional review boards of Stanford Hospital and Clinics and the Kaiser Permanente Hospital, South Sacramento will review and approve this study prior to initiation. All patient information will be kept confidential in accordance with HIPAA and only the study coordinator and the protocol director will have access to the data.

Inclusion/Exclusion Criteria

All ankle fractures that undergo open reduction internal fixation of the medial malleolus in adults at or over 18 years-of-age will be considered for inclusion.

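### Preference-only removals are not separated from the removal endpoint, so unmasked preference could create an arm difference without a symptom difference

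*Combined protocol and SAP*

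**What the plan says.** All references are to the combined protocol and SAP.

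- **Criteria for Removal of Hardware.** The general rule is "Hardware may be removed if there is a surgical indication or patient/surgeon preference for removal". For patients with sensitivity that does not bother them, "they should not be subjected to hardware removal unless by patient or surgeon preference and noted as medial or lateral hardware removed for preference". Bothersome sensitivity is rated 0–5, leads to removal and is noted as removal for sensitivity. Infection, non-union and mal-union are the other listed indications. The section also requires that "The location of symptoms and reason for hardware removal should be specified and documented".
- **Study Objectives (study summary table).** The primary objective is less medial hardware pain "reducing the incidence of hardware removal from the medial malleolus at one year after sustaining an ankle fracture".
- **Specific Aims.** Aim 4 reads "Prospectively establish superiority with respect to the hardware removal rate after Acutrak headless compression screw fixation", compared with other fixation methods. No reason for removal is named.
- **Power Analysis and Statistics.** The calculation uses the overall removal rate, 24% against 14.5%, with 424 patients. The 24% combines 6% (8/126) non-pain removals and 17% (22/126) pain removals. The same paragraph ends: "Medial hardware removal will be prohibited for lateral hardware pain".
- **Background, before the Hypothesis.** The headless design "may obviate the need for hardware removal".
- **Randomization and Statistical Methods.** Allocation is by sealed envelope, and no masking of patient, surgeon or assessor is described. The analysis is left to an appropriate test, with nothing said about analysis by reason for removal.

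**The concern.** The trial's argument is a chain: less prominent hardware, less medial pain, fewer removals. A removal done by preference in a patient without bothersome symptoms lies outside that chain, yet nothing keeps it out of the event count.

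Preference is also the reason most open to knowledge of the implant. The operating surgeon must know which device is in place, and the protocol tells surgeons that the headless screw is expected to make removal unnecessary. Patients may know as well. If preference removals are commoner with headed screws, plates and wires, the comparison moves towards Acutrak. Randomization does not prevent this, because the difference arises after allocation. A larger sample does not help either, because it makes the same bias more likely to reach significance.

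At stake is whether a significant primary result could be read as a reduction in symptom-driven removal, which is what the primary objective describes.

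**Working it through.** **1. Which removals count.** Four places bear on this.

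- Criteria for Removal: preference is an allowed reason and is recorded as such.
- Primary objective: medial removal at one year, introduced through pain, with no list of qualifying reasons.
- Aim 4: removal rate, no reason given.
- Power section: overall rate, including non-pain removals.

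None excludes preference removals, and none expressly includes them. The plan has no event definition by reason.

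**2. The plan's own figure.** The rates are p1 = 0.24 and p2 = 0.145, with mean 0.1925, alpha 0.05 and power 80%. A 1:1 ratio is assumed because none is stated.

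n per arm = [z_α·√(2·p̄·(1−p̄)) + z_β·√(p1(1−p1) + p2(1−p2))]² / (p1−p2)²

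- One-sided: (0.9171 + 0.4658)² / 0.095² = 211.9, so 212 per arm and 424 in total. This matches the plan.
- Two-sided: (1.0928 + 0.4658)² / 0.095² = 269.2, so 270 per arm and 540 in total.

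The 424 therefore fits a one-sided 5% test. The plan does not state sidedness, so both versions are shown below.

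**3. Illustration of the bias.** Inputs:

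- 212 per arm, from the plan (424/2).
- Symptom-driven removal of 17% in both arms, meaning no true effect. The 17% is borrowed from the power section, where it is pain removal on either side of the ankle at 6 months.
- Preference removals by arm: **assumed**, because the documents give none.

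Chance of significance favouring Acutrak = 1 − Φ[(z·s0 − d)/s1], where d = p1 − p2, s0 = √(2·p̄·(1−p̄)/n) and s1 = √(p1(1−p1)/n + p2(1−p2)/n). The opposite tail is Φ[(−z·s0 − d)/s1].

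Worked case, preference removals 7% vs 2%, so 24% vs 19%: s0 = 0.03990 and s1 = 0.03983. Then (1.96 × 0.03990 − 0.05)/0.03983 = 0.708, and 1 − Φ(0.708) = 0.239. The other tail is 0.0006, for a total of 0.240.

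| Control excess | Control vs Acutrak | Two-sided 0.05, total | of which favours Acutrak | One-sided 0.05 |
|---|---|---|---|---|
| 0 | 17% vs 17% | 5% | 2.5% | 5% |
| 1 point | 18% vs 17% | 6% | 5% | 8% |
| 2 points | 19% vs 17% | 8% | 8% | 13% |
| 3 points | 21% vs 18% | 12% | 12% | 19% |
| 5 points | 24% vs 19% | 24% | 24% | 35% |
| 5 points | 27% vs 22% | 22% | 22% | 33% |

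A 5-point excess is 5/9.5 = 53% of the planned effect. A 1-point excess hardly matters.

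**4. The lateral-pain sentence.** The prohibition appears only in the power section. The preference rule is in the criteria section, where removals are noted as medial or lateral. Neither refers to the other. A patient with lateral pain whose medial hardware is also removed, with preference as the recorded reason, is not clearly covered by either text.

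**The case against.** - **Nothing says that preference removals count.** The primary objective is tied to medial hardware pain, and the pain and non-pain components of the powered rate do not name preference. This stands in part: inclusion is inferred from silence. But the objective lists no qualifying reasons and the powered rate is overall removal, so a narrower reading is possible without being specified. Recording the reason is not a rule for analysing it.
- **For symptomatic patients the trigger is the patient's answer, not the surgeon's discretion.** This stands. All bothersome sensation leads to removal under the criteria section, so the concern is confined to preference-only removals.
- **The lateral-pain prohibition is categorical.** A reader might infer that preference is a permitted way around it. The documents do not support that: nothing authorizes recording a lateral-pain removal as medial preference. What remains is two rules that are not reconciled.
- **The gaps are assumed, and always against control.** This stands. The figures show sensitivity to a gap and are no evidence that one will occur.
- **Restricting events by reason does not remove the bias.** The same unmasked surgeons and patients supply the reason, and a preference removal can be recorded as sensitivity. This stands, and it is why neither analysis should stand alone.

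**Conclusion.** The concern holds in a limited form. Preference is an allowed reason for removal without bothersome symptoms, the endpoint and the powered rate are not restricted by reason, and no masking is described. A difference in preference between arms could therefore produce a difference in the primary endpoint without a difference in symptoms.

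Its size is unknown. Under the stated assumptions, the chance of a significant result rises from 5% to about 6%, 8%, 12% or 22–24% for a control excess of 1, 2, 3 or 5 points, nearly all of it favouring Acutrak from 2 points upward. The assumptions are equal symptom-driven removal of 17%, 212 per arm, 1:1 allocation and a two-sided test. The 17% covers either side of the ankle at 6 months, whereas the endpoint is medial at one year.

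A reader might go further and infer that the plan expressly counts preference removals, or that a bias towards Acutrak has been shown. The documents support neither: the first is silence, and the second would need preference rates that they do not give. The point deserves correction because it touches the primary endpoint and the reason for each removal is already to be recorded.

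**What to change.** 1. State in the statistics section which recorded reasons make a removal a primary event.
2. Pre-specify two medial analyses: all-cause removal, and removal for sensitivity, infection, non-union or mal-union. Name one as primary and the other as the key sensitivity analysis. Require the two to agree before concluding that Acutrak reduces symptom-driven removal.
3. Tabulate preference-only medial removals by arm, including those done during a lateral removal.
4. Record the patient's answer on bothersome sensitivity before the removal decision is recorded.
5. Reconcile the preference rule in the criteria section with the lateral-pain sentence in the power section. Which of them governs is for the investigators to settle.

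The cost is statistical wording, one table and one ordering requirement on the form. Reason and location are already to be documented. The restricted analysis will have slightly fewer events. Preference removals can also pre-empt later symptomatic ones, which is why the all-cause analysis is kept alongside it. None of this removes the subjectivity of the recorded reason, but it makes any imbalance visible.

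### Removal for sensitivity follows from the patient's own answer and no masking of patients or callers is described, so expectation could produce or inflate part of the medial pain and removal difference

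*Combined protocol and SAP*

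**What the plan says.** **The trigger.** Criteria for Removal of Hardware says "Patients will be asked whether they feel bothersome sensitivity at the both medial and lateral malleolus". Bothersome sensation is graded 0 to 5, and then "All bothersome sensation will be subjected to hardware removal and noted as removal for sensitivity". No intensity threshold, examination finding or adjudication stands between the answer and the event. A separate preference route exists: "Hardware may be removed if there is a surgical indication or patient/surgeon preference for removal". Location and reason must be documented.

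**Allocation.** Randomization says "Patients will be randomized by sealed envelope to surgical fixation with traditional headed screws, plates, and wires or Acutrak headless compression screws". Neither that section nor the Acumed Study Summary describes masking of patient, surgeon or assessor.

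**Timing.** The primary objective in the Acumed Study Summary is medial hardware pain and medial removal at one year. Under Follow-up Protocol and Table 1, the 6-month and one-year contacts are by telephone and mail, with VAS pain taken by telephone.

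**The expected direction.** The Hypothesis states that "lack of prominent hardware surfaces will reduce the incidence and severity of hardware related pain".

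**Lateral data.** Table 1 schedules "Lateral Ankle Tenderness" and VAS pain by location at every contact. Power Analysis and Statistics gives lateral pain one role, as an attribution rule: "Medial hardware removal will be prohibited for lateral hardware pain". No lateral comparison between arms is planned.

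**The concern.** The surgeon must know the implant. The patient need not, and the caller need not either. If patients know, those with a headless screw may be readier to call a sensation minor, and those with a plate or headed screws readier to call it bothersome. Under the removal rule that answer becomes a removal coded for sensitivity. Separating out preference removals therefore does not deal with the problem, because the shift sits inside the category that the trial would treat as genuine symptoms.

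Specific Aims 3 and 4, superiority on hardware pain and on hardware removal, both rest on this report. The trial already collects lateral pain, which the randomized medial implant should have little reason to change, but the plan makes no use of it as a check on reporting.

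**Working it through.** **1. The plan's own figure.** Inputs from Power Analysis and Statistics: 24% versus 14.5%, alpha 0.05, power 80%, 424 patients. Equal allocation is assumed. With mean rate 0.1925,

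n per arm = [z_α·√(2 × 0.1925 × 0.8075) + 0.8416·√(0.24 × 0.76 + 0.145 × 0.855)]² / 0.095²

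- One-sided (z = 1.645): 211.9, so 212 per arm and 424 in total, which matches.
- Two-sided (z = 1.960): 269.2, so 270 per arm and 540 in total.

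The plan does not state sidedness, so both are carried below. The point here does not depend on which was meant.

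**2. How much of the endpoint depends on pain.** From the cited retrospective series: pain removals 22/126 = 17.5%, non-pain 8/126 = 6.3%, total 30/126 = 23.8%. Pain accounts for 22/30 = 73% of removals. The 22 pool medial and lateral pain at 6 months, and the documents give no medial-only count and no one-year count.

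**3. Spurious difference with no device effect.** Let f be the share of pain removals that depends on expectation. The documents give no value, so f = 10% to 30% is an assumption. Difference d = f × pain-removal rate.

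| f | Pooled base, 22/126 | Share of 9.5 | If half were medial, 11/126 (assumption) | Share of 9.5 |
|---|---|---|---|---|
| 10% | 1.7 points | 18% | 0.9 points | 9% |
| 20% | 3.5 points | 37% | 1.7 points | 18% |
| 30% | 5.2 points | 55% | 2.6 points | 28% |

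On the pooled base, the whole planned effect would need f = 0.095 / 0.1746 = 54%.

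**4. Effect on the false-positive rate.** With 212 per arm, control rate p₁ = 30/126 and headless-arm rate p₂ = p₁ − d, the probability of a significant result favouring the headless screw is Φ[(d − z·SE₀)/SE₁]. Here SE₀ = √(2·p̄(1−p̄)/212), SE₁ = √([p₁(1−p₁) + p₂(1−p₂)]/212), and p̄ is the mean of the two rates. The two-sided figure adds the opposite tail.

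Example, f = 30% on the pooled base: p₂ = 0.1857, d = 0.0524, SE₀ = 0.0397, SE₁ = 0.0396. One-sided: Φ[(0.0524 − 1.645 × 0.0397)/0.0396] = 37%.

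| f | Pooled base: one-sided / two-sided | Half medial: one-sided / two-sided |
|---|---|---|
| 0% | 5% / 5% | 5% / 5% |
| 10% | 11% / 7% | 8% / 6% |
| 20% | 22% / 14% | 11% / 7% |
| 30% | 37% / 26% | 16% / 10% |

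A shift well short of 9.5 points is enough to disturb the nominal 5%.

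**The case against.** The strongest reply has four parts.

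- **Size.** A reader might infer that expectation alone could explain a positive result, or that such a result would be indistinguishable from expectation. The documents do not support that. They give no size for the effect, the range for f is assumed, and 54% of pooled pain removals would have to depend on expectation to give 9.5 points. The pooled base also overstates the part that concerns the medial side. This stands, and is why the claim is limited to part of the difference.
- **Silence.** A reader might also infer a declared open-label design. The plan declares nothing either way, and consent pages are not in the material available for review. What can be said is that no masking is described.
- **Existing safeguards.** The plan separates bothersome from non-bothersome sensation and preference from sensitivity, grades intensity, and has clinical tenderness examinations through 3 months. These help description. They do not stop an informed patient from answering differently, and the VAS at one year is by telephone.
- **Limits of a lateral check.** Eligibility does not require lateral hardware, and expectation about a medial implant need not spread to the lateral side. Lateral-only removal would be a poor control, because a patient counts there only if the medial hardware stays in, so a real device effect could itself make the arms differ. A rule that automatically reads a lateral difference as reporting bias would be too strong. These points stand and shape the fix.

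**Conclusion.** The concern holds in limited form. The removal trigger is the patient's report, pain at the primary timepoint is collected by telephone, and no masking of patients or callers is described. Expectation could therefore produce or inflate part of the medial pain and removal difference and raise the false-positive rate.

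For removal, the illustrative size is 1.7 to 5.2 points on the pooled 6-month base, or 0.9 to 2.6 points if half of those removals were medial. Both ranges rest on the assumed 10% to 30% share, on 6-month rates standing in for one year, and on 212 patients per arm for the false-positive figures. They show what the design leaves open and do not estimate a bias known to be present. The change should be made before enrolment, since a patient who has been told the implant cannot be masked afterwards.

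**What to change.** 1. **Masking.** State in the protocol and consent that patients are not told which medial implant was used until the one-year contact is complete. Where existing staffing allows, state that the coordinator making the 6-month and one-year calls does not consult the Operative/Device record beforehand. The cost is wording, with no added staff. The downside is that masking will be partial: films, palpable hardware or the coordinator's earlier role may reveal the implant.

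2. **Supportive lateral check.** Pre-specify a between-arm comparison of lateral VAS pain and lateral bothersome sensitivity, reported overall and among patients with lateral hardware. State its reading in advance: a lateral difference would suggest reporting bias, but its absence would not rule out expectation specific to the medial side. Leave out lateral-only removal and attach no automatic rule for interpretation. The cost is one extra table from data already scheduled, plus a record of who has lateral hardware if the operative form does not already capture it.
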